7.3 Labelling and shipment of biohazard samples

The Principal Investigator ensures that samples are labelled and shipped in accordance with the Laboratory Manual and the Biological Substance, Category B Regulations (materials containing or suspected to contain infectious substances that do not meet Category A criteria), see [Appendix C](#) 'IATA 6.2 Guidance Document'.

Any samples identified as Infectious Category A materials are not shipped and no further samples will be taken from the patient unless agreed with AstraZeneca and appropriate labelling, shipment and containment provisions are approved.

7.4 Chain of custody of biological samples

A full chain of custody is maintained for all samples throughout their lifecycle.

The Principal Investigator keeps full traceability of collected biological samples from the patients while in storage at the centre until shipment or disposal (where appropriate) and keeps documentation of receipt of arrival.

The sample receiver keeps full traceability of the samples while in storage and during use until used or disposed of or until further shipment and keeps documentation of receipt of arrival.

AstraZeneca keeps oversight of the entire life cycle through internal procedures, monitoring of study sites and auditing of external laboratory providers.

Samples retained for further use are registered in the AstraZeneca biobank system during the entire life cycle.

7.5 Withdrawal of informed consent for donated biological samples

If a patient withdraws consent to the use of donated biological samples, the samples will be disposed of/destroyed, and the action documented. If samples are already analysed, AstraZeneca is not obliged to destroy the results of this research.

As collection of the biological sample is an optional part of the study, then the patient may continue in the study after this consent is withdrawn.

The Principal Investigator:

- Ensures patients' withdrawal of informed consent to the use of donated samples is notified immediately to AstraZeneca.
- Ensures that biological samples from that patient, if stored at the study site, are immediately identified, disposed of /destroyed, and the action documented.
- Ensures the laboratory(ies) holding the samples is/are informed about the withdrawn consent immediately and that samples are disposed/destroyed, the action documented and the signed document returned to the study site.
- Ensures that the patient and AstraZeneca are informed about the sample disposal.

AstraZeneca ensures the central laboratory(ies) holding the samples is/are informed about the withdrawn consent immediately and that samples are disposed of/destroyed and the action documented and returned to the study site.

8. ETHICAL AND REGULATORY REQUIREMENTS

8.1 Ethical conduct of the study

The study will be performed in accordance with ethical principles that have their origin in the Declaration of Helsinki and are consistent with ICH/Good Clinical Practice, applicable regulatory requirements and the AstraZeneca policy on Bioethics and Human Biological Samples.

8.2 Patient data protection

The Informed Consent Form will incorporate (or, in some cases, be accompanied by a separate document incorporating) wording that complies with relevant data protection and privacy legislation.

Patient data protection for the pharmacogenetic research part of the study is described in [Appendix D](#).

8.3 Ethics and regulatory review

An Institutional Review Board (IRB) should approve the final study protocol, including the final version of the Informed Consent Form and any other written information and/or materials to be provided to the patients. The investigator will ensure the distribution of these documents to the applicable IRB, and to the study site staff.

The opinion of the IRB should be given in writing. The investigator should submit the written approval to AstraZeneca before enrolment of any patient into the study.

The IRB should approve all advertising used to recruit patients for the study.

AstraZeneca should approve any modifications to the Informed Consent Form that are needed to meet local requirements.

If required by local regulations, the protocol should be re-approved by the IRB annually.

Before enrolment of any patient into the study, the final study protocol, including the final version of the Informed Consent Form, is approved by the national regulatory authority or a notification to the national regulatory authority is done, according to local regulations.

AstraZeneca will handle the distribution of any of these documents to the national regulatory authorities.

AstraZeneca will provide Regulatory Authorities, IRBs and Principal Investigators with safety updates/reports according to local requirements.

Each Principal Investigator is responsible for providing the IRB with reports of any serious and unexpected adverse drug reactions from any other study conducted with the investigational product. AstraZeneca will provide this information to the Principal Investigator so that he/she can meet these reporting requirements.

8.4 Informed consent

The Principal Investigator(s) at each centre will:

- Ensure each patient is given full and adequate oral and written information about the nature, purpose, possible risk and benefit of the study.

- Ensure each patient is notified that they are free to discontinue from the study at any time.
- Ensure that each patient is given the opportunity to ask questions and allowed time to consider the information provided.
- Ensure each patient provides signed and dated informed consent before conducting any procedure specifically for the study.
- Ensure the original, signed Informed Consent Form(s) is/are stored in the Investigator's Study File.
- Ensure a copy of the signed Informed Consent Form is given to the patient.
- Ensure that any incentives for patients who participate in the study as well as any provisions for patients harmed as a consequence of study participation are described in the informed consent form that is approved by an IRB.

8.5 Changes to the protocol and informed consent form

Study procedures will not be changed without the mutual agreement of the Principal Investigator, Investigator and AstraZeneca.

If there are any substantial changes to the study protocol, then these changes will be documented in a study protocol amendment and where required in a new version of the study protocol (Revised Clinical Study Protocol).

The amendment should be approved by each IRB and if applicable, also the national regulatory authority, before implementation. Local requirements should be followed for revised protocols.

AstraZeneca will distribute any subsequent amendments and new versions of the protocol to each Principal Investigator(s). For distribution to IRB see Section 8.3.

If a protocol amendment requires a change to a centre's Informed Consent Form, AstraZeneca and the centre's IRB should approve the revised Informed Consent Form before the revised form is used.

If local regulations require, any administrative change will be communicated to or approved by each IRB.

8.6 Audits and inspections

Authorised representatives of AstraZeneca, a regulatory authority, or an IRB may perform audits or inspections at the centre, including source data verification. The purpose of an audit or inspection is to systematically and independently examine all study-related activities and documents, to determine whether these activities were conducted, and data were recorded,

analysed, and accurately reported according to the protocol, Good Clinical Practice (GCP), guidelines of the International Conference on Harmonisation (ICH), and any applicable regulatory requirements. The investigator will contact AstraZeneca immediately if contacted by a regulatory agency about an inspection at the centre.

9. STUDY MANAGEMENT BY ASTRAZENECA

9.1 Pre-study activities

Before the first patient is entered into the study, it is necessary for a representative of AstraZeneca to visit the investigational study site to:

- Determine the adequacy of the facilities.
- Determine availability of appropriate patients for the study.
- Discuss with the investigator(s) (and other personnel involved with the study) their responsibilities with regard to protocol adherence, and the responsibilities of AstraZeneca or its representatives. This will be documented in a Clinical Study Agreement between AstraZeneca and the investigator.

9.2 Training of study site personnel

Before the first patient is entered into the study, an AstraZeneca representative will review and discuss the requirements of the Clinical Study Protocol and related documents with the investigational staff and also train them in any study specific procedures and the system(s) utilised.

The Principal Investigator will ensure that appropriate training relevant to the study is given to all of these staff, and that any new information relevant to the performance of this study is forwarded to the staff involved.

The Principal Investigator will maintain a record of all individuals involved in the study (medical, nursing and other staff).

9.3 Monitoring of the study

During the study, an AstraZeneca representative will have regular contacts with the study site, including visits to:

- Provide information and support to the investigator(s).
- Confirm that facilities remain acceptable.
- Confirm that the investigational team is adhering to the protocol, that data are being accurately and timely recorded in the CRFs, that biological samples are handled in

accordance with the Laboratory Manual and that investigational product accountability checks are being performed.

- Perform source data verification (a comparison of the data in the CRFs with the patient's medical records at the hospital or practice, and other records relevant to the study) including verification of informed consent of participating patients. This will require direct access to all original records for each patient (eg, clinic charts).
- Ensure withdrawal of informed consent to the use of the patient's biological samples is reported and biological samples are identified and disposed of/destroyed accordingly, and the action is documented, and reported to the patient.

The AstraZeneca representative will be available between visits if the investigator(s) or other staff at the centre needs information and advice about the study conduct.

9.3.1 Source data

Source data locations are specified in the Clinical Study Agreement.

9.4 Study agreements

The Principal Investigator at each/the centre should comply with all the terms, conditions, and obligations of the Clinical Study Agreement for this study. In the event of any inconsistency between this Clinical Study Protocol and the Clinical Study Agreement, the terms of Clinical Study Protocol shall prevail with respect to the conduct of the study and the treatment of patients and in all other respects, not relating to study conduct or treatment of patients, the terms of the Clinical Study Agreement shall prevail.

Agreements between AstraZeneca and the Principal Investigator should be in place before any study-related procedures can take place, or patients are enrolled.

9.4.1 Archiving of study documents

The Investigator follows the principles outlined in the Clinical Study Agreement.

9.5 Study timetable and end of study

The end of the study is defined as "the last visit of the last patient undergoing the study".

The study is expected to start in

The study may be terminated at the centre if the study procedures are not being performed according to GCP, or if recruitment is slow. AstraZeneca may also terminate the entire study prematurely if concerns for safety arise within this study or in any other study with AZD3355.

The recruitment period will end when the targeted number of randomised patients has been reached. Individual investigators will be notified by AstraZeneca.

10. DATA MANAGEMENT BY COGNIZANT DMC

The CRF and the clinical database is created in accordance with Cognizant standard operating procedures using existing project standards. CRF instructions are provided to sites for recording data. The data are entered, verified and cleaned and data sets prepared according to Cognizant procedures. The data management staff is responsible for conducting and/or overseeing the following information.

Data Management Plan (DMP)

The study DMP will describe the methods used to collect, check and process clinical data in detail. It will also clarify the roles and responsibilities for the different functions and personnel involved in the data management process.

Dictionary coding

Medical coding is done using the most current version of MedDRA and AstraZeneca Drug Dictionary.

Management of external data

Data Management determines the format of the data to be received from external vendors and coordinates the flow of data to an external environment or clinical database (if applicable). Data Management will ensure that the data collection tool will be tested/validated as needed. External data reconciliation will be done with the clinical database as applicable.

Serious Adverse Event (SAE) Reconciliation

SAE reconciliation reports are produced and reconciled with Patient Safety database and/or the Investigational Site.

Quality Control Process

Data Management performs the quality control of the data in accordance with the Cognizant SOPs. Clean file occurs when all data have been declared clean.

Genotype Data

Genotype data generated in this study will be stored in the AstraZeneca genotyping LIMS database, or other appropriate secure system, separate from the database used for the main study.

Some or all of the clinical datasets from the main study may be merged with the genetic data in a suitable secure environment separate from the clinical database. The results from this genetic research will be reported separately from the clinical study report for the main study.

11. EVALUATION AND CALCULATION OF VARIABLES BY ASTRAZENECA

11.1 Calculation or derivation of efficacy variable(s)

11.1.1 Impedance/pH measurements

In this study the following parameters will be studied for the total period, as well as for periods with upright and supine position:

1. Total number of reflux episodes
2. Number and percentage of registration time of acid reflux episodes ($\text{pH} < 4$)
3. Number and percentage of registration time of weakly acidic reflux episodes ($4 \leq \text{pH} < 6.5$)
4. Number and percentage of registration time of weakly alkaline reflux episodes ($\text{pH} \geq 6.5$)
5. Number and percentage of liquid reflux episodes
6. Number and percentage of gas reflux episodes
7. Number and percentage of mixed gas/liquid reflux episodes
8. Number and proportion of reflux events (liquid, gas or mixture) with proximal extent
9. The percentage of time with intragastric $\text{pH} < 4$ during the 24-hour period at 10 cm below LES
10. The relation between reflux episodes, acid- and weakly acid or weakly alkaline reflux and GERD symptoms during 24 hours (Symptom Index (SI), Symptom associated probability (SAP))
11. Mean bolus clearance time (sec)

11.1.2 Definition of variables

- An episode with acid reflux is defined as an episode with an intra-esophageal $\text{pH} < 4$ lasting longer than 5 seconds. If pH is already below 4 a further fall in pH of at least one pH unit lasting longer than 5 seconds is required.
- Weakly acidic reflux is defined as a reflux episode with an intra-esophageal pH between 4 and 6.5 lasting longer than 5 seconds.

- Weakly alkaline reflux is defined as a reflux episode, lasting longer than 5 seconds, during which the intra-esophageal pH does not drop below 6.5.
- A liquid reflux episode is defined as an episode of reflux that manifested as a drop in the impedance (in Ohms) of more than 50% from its baseline, and propagates aborally at least two impedance measurement segments from the most distal channel.
- A gas reflux episode is defined as an episode of reflux that is associated with an rapid (3000 Ω /s) increase in the impedance level (>5000 Ω) from the baseline level, and propagates aborally at least two impedance measurement segment from the most distal channel in the absence of swallowing.
- A mixed gas/liquid reflux episode is defined as an episode of reflux in which there is a combination of liquid and gas criteria in the same time period.
- Proximal extent of the refluxate is defined as the number of reflux events reaching the most proximal impedance measuring site
- Acid clearance time is defined as the mean total duration of an acid reflux episode and will be calculated as the total time with pH<4 divided by the total number of acid reflux episodes.
- Bolus clearance time (sec) is defined as the time in seconds from the drop in impedance to below 50% of baseline until impedance has recovered to above 50% of baseline.
- Symptoms reported as GERD related by the patients on the diary card

11.1.3 Symptom analysis variables

During the 24 hours of ambulatory impedance/pH measurement, time for possible GERD symptoms, meal intake and periods in supine position will be recorded by the patient using the data logger. On the diary card the patient will also be recording the type of GERD symptoms.

Each time the patient records a symptom it is counted as a symptom episode. The type of the episode is determined by the specific type of symptom that occurred during the recording.

Symptom Index (SI)

For calculation of symptom index, symptoms will be identified on the impedance/pH tracing time line. Symptoms associated with a reflux event occurring within a 2 minute window before and 2 minute window after the symptom will be considered reflux positive. SI is calculated by the number of reflux positive symptoms divided by the number of symptoms (50% or more is considered to support a positive correlation between symptoms and reflux) ([Wiener et al 1988](#)).

Symptom associated probability (SAP)

For calculation of SAP, consecutive two minute periods of pH recording will be analysed for the presence of reflux and symptoms. A symptom episode will be considered as reflux positive if either of the two minute periods preceding or following the start of the symptom was reflux positive (pH<4 for ≥ 5 seconds). A contingency table will be constructed and Fisher's exact test will be used to calculate the p value according to Weusten et al. SAP was calculated as $(1.0-P) \times 100\%$ and a value greater than 95% is considered to support a positive correlation between symptoms and reflux. (Weusten et al 1994)

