3.2 Rationale for study design, doses and control groups

The doses were selected in order to evaluate the effect of AZD3355 in a dose range from 30 mg to 240 mg bid, in order to evaluate doses both higher and lower than the 65 mg bid dose that was used in study [D9120C00020](#). The 240 mg bid dose was chosen in order to evaluate the effect at the highest possible therapeutic dose. In order to estimate the efficacy and compare and assess safety information for AZD3355 each patient will receive placebo in addition to 3 of the 4 doses of AZD3355.

The study population was chosen to resemble the study population in [D9120C00020](#) which allowed mild symptoms for three days. Therefore, the study population will not be exactly comparable with the study population in the planned dose finding study ([D9120C00019](#)) where only patients with persistent symptoms of moderate severity will be included. Although symptoms are not the primary endpoint to this study, the information on the effect of AZD3355 on reflux episodes is still valuable in understanding if there is a dose relationship in patients who have reflux irrespective of the symptom burden.

The double-blind, cross over design was chosen in order to avoid bias and reduce variability and thereby sample size. Placebo was included as a comparator to determine the difference between PPI alone and the addition of AZD3355. The sample size was based on previous experience in a similar setting.

The effect on reflux as measured by 24h combined impedance/pH registration was chosen as primary endpoint since it is believed that AZD3355 reduces the total number of reflux episodes, whether the reflux is acid, weakly acidic or weakly alkaline. Symptoms are thought to be produced by the refluxate in the esophagus therefore, decreasing the number of reflux episodes should impact on the symptom burden of patients who have GERD and are partial responders to PPI treatment. Further, intragastric pH will be monitored to evaluate if AZD3355 has an effect on gastric acid secretion, as has been suggested in some animal studies, and can reduce the time with pH<4 in the dose range used in the study.

Genetic samples will be collected for future exploratory research into genes/genetic variation that may influence response (ie, PK profile, safety, tolerability and efficacy) to AZD3355 and/or agents used in combination and/or as comparators and/or susceptibility to GERD.

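### Section 11.1.3 gives a symptom two 2-minute periods in which to match reflux but widens no symptom-free unit, so the symptom association probability passes 95% by chance more often than an equal-window test would

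*Protocol*

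**What the plan says.** Section 11.1.3 defines two measures of the relation between reflux and symptoms. Section 11.1.1 (item 10) names both, and they serve a secondary objective in section 2.2. SAP here means the symptom association probability, not the statistical analysis plan.

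- **SAP, unit:** "consecutive two minute periods of pH recording will be analysed for the presence of reflux and symptoms".
- **SAP, symptom rule:** a symptom episode is positive "if either of the two minute periods preceding or following the start of the symptom was reflux positive", with positive defined as pH below 4 for at least 5 seconds.
- **SAP, test and cut-off:** "A contingency table will be constructed and Fisher's exact test will be used to calculate the p value", following a cited method paper. SAP is (1 - P) x 100%, and "a value greater than 95% is considered to support a positive correlation between symptoms and reflux".
- **Symptom Index (SI):** a reflux event "within a 2 minute window before and 2 minute window after the symptom will be considered reflux positive". SI is the share of symptoms that are positive, and "50% or more is considered to support a positive correlation between symptoms and reflux". No test is attached to it.

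The section does not say how the symptom-free row of the SAP table is formed, or whether the test is one- or two-sided.

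**The concern.** Fisher's exact test asks whether symptom units are reflux positive more often than symptom-free units. The comparison is fair only if both kinds of unit have the same opportunity to be positive. Under the stated rule a symptom has two periods and a symptom-free unit, read as one consecutive period, has one. Even with no association the symptom row is then positive nearly twice as often, and the test can report an association that the scoring created.

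At stake is the meaning of the 95% cut-off for a secondary variable. This is not a detail left to the statistical analysis plan: the protocol itself fixes the unit, the symptom rule, the test and the cut-off, and their combination is the difficulty.

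**Working it through.** **Inputs**

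- Periods: 24 h x 60 / 2 = 720 (600 for the 20 h minimum in section 6.3.1.1).
- Nominal error: SAP above 95% means P < 0.05. The protocol states no achieved error rate, so there is no figure to reproduce.
- Reflux density p, the share of positive periods. Section 12.3 gives a geometric mean of 30.6 episodes per 24 h on AZD3355, and 30.6/720 = 4.25%. Section 1.3 gives a ratio to placebo of 0.61, so placebo is about 30.6/0.61 = 50.2, and 50.2/720 = 7.0%. Both assume one period per episode and cover all reflux types. A sparser 2% is added as an assumption.
- Symptoms per recording, k: not in the protocol. Values of 3 to 20 are assumed.

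**Formula.** With no association and independent periods, a symptom-free period is positive with probability p and a symptom with probability q = 1 - (1 - p)^2.

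- p = 2%: q = 3.96%
- p = 4.25%: q = 8.32%
- p = 7%: q = 13.51%

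**One case by hand.** Take p = 7% and k = 10, so about 50 of 710 symptom-free periods are positive. Two positive symptoms give Fisher P = 0.159 and three give P = 0.031, so three are needed. The chance of three or more out of 10 is 2.8% at probability 7% and 14.3% at 13.51%. Averaging over the varying symptom-free count gives 2.7% and 13.6%.

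**All cases.** Exact sum over binomial counts, with k symptoms and 720 - k symptom-free periods. Entries are the chance of P < 0.05 in the positive direction; one- and two-sided tests agree to the decimals shown.

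| p | k | equal windows (2 min each) | rule as written | ratio |
|---|---|---|---|---|
| 2% | 3 | 1.4% | 3.0% | 2.1 |
| 2% | 5 | 0.5% | 1.6% | 3.4 |
| 2% | 10 | 1.6% | 5.7% | 3.5 |
| 2% | 20 | 2.1% | 8.0% | 3.9 |
| 4.25% | 3 | 0.5% | 2.0% | 3.7 |
| 4.25% | 5 | 1.7% | 5.8% | 3.5 |
| 4.25% | 10 | 1.6% | 6.7% | 4.3 |
| 4.25% | 20 | 2.4% | 13.1% | 5.6 |
| 7% | 3 | 1.4% | 5.0% | 3.6 |
| 7% | 5 | 3.1% | 10.2% | 3.4 |
| 7% | 10 | 2.7% | 13.6% | 5.1 |
| 7% | 20 | 2.8% | 19.8% | 7.0 |

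**Sensitivity, by simulation**

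- Clustered reflux (two-state Markov chain, persistence 0.3 to 0.7, p from 4.25% to 10%, k from 5 to 20): 0.8-3.1% with equal windows, 2.7-19.4% as written. At the strongest clustering (0.7) the as-written range is 2.7-8.4%.
- Episodes in continuous time (30.6 or 50.2 per day, mean length 0.5 to 4 minutes, k from 5 to 20): 1.3-3.5% with the preceding 2 minutes only, 3.5-16.7% as written.
- 4-minute units in both rows, independent periods: 0.6-3.7%.

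**Symptom Index, for comparison.** The chance match per symptom is 1 - exp(-rate x window). At 50.2 episodes it is 6.7% for 2 minutes and 13.0% for 4; at 30.6 it is 4.2% and 8.1%. The chance that SI reaches 50% with the 4-minute window at 50.2 episodes is 4.6% with 3 symptoms, 1.8% with 5 and 0.5% with 10.

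**The case against.** **The symptom-free row is inferred.** The section never spells it out and refers to a method paper that is not at hand. This stands as a limit on certainty. But the text names one unit, the consecutive 2-minute period, and a second only for symptoms, so the unequal reading is the natural one. If another construction is meant, the section should state it.

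**The absolute rate is often modest.** This stands. A reader might infer that SAP above 95% generally occurs several times more often than 5%. The table does not support that: several cells lie at or below 5%. The multiples are against an equal-window Fisher test, which is itself conservative.

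**The densities do not match the signal.** This stands too. The counts of 30.6 and 50.2 cover all reflux, whereas this SAP counts only pH below 4 in patients on continuous PPI treatment (section 4.1, criterion 7). The true p may be lower, or higher if long acid episodes fill several periods.

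**Reflux after the symptom.** Section 3.2 says "Symptoms are thought to be produced by the refluxate in the esophagus", so a reader might infer that the following period can never hold the cause. On a fixed grid the onset usually falls inside a period, and if that period is the one called following, part of it precedes the symptom. The finding rests on unequal windows, not on this argument.

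**The Symptom Index.** A reader might extend the point to SI because it uses the same 4 minutes. SI has no test and no error rate to inflate, and at its 50% cut-off the chance rates above are small. Nor does narrowing the window stop SI from falling with the reflux count: the chance match drops by about 38% from 50.2 to 30.6 episodes with either window (13.0% to 8.1%, or 6.7% to 4.2%). That the drug would be misread as uncoupling symptoms from reflux is speculation.

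**Conclusion.** The point holds for the SAP. On the natural reading of section 11.1.3 the symptom and symptom-free units have unequal windows, and with no true association the chance of SAP above 95% is about 2 to 7 times the equal-window rate under independent periods. In absolute terms it is mostly about 2-6% with few symptoms or sparse reflux (the exceptions in the table are 8.0% for 20 symptoms at 2%, and 10.2% for 5 symptoms at 7%). It is about 7-20% with 10 to 20 symptoms at 4-7% positive periods. Clustering lowers the inflation but did not remove it in any case tried.

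The direction follows from the rule. The size rests on assumed symptom counts and on densities from all-type reflux. Only a secondary symptom-association variable is touched. The primary dose-response analysis and the comparisons of each dose with placebo on reflux counts (section 12.2) are not.

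**What to change.** In section 11.1.3, score symptom and symptom-free units for the SAP over the same span. Either option serves:

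- a symptom unit is the 2 minutes before onset, and a symptom-free unit is one 2-minute period; or
- both kinds of unit span 4 minutes, which keeps the protocol's window around the symptom.

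Add a sentence on how the table is built: what a symptom-free unit is, and how the period containing the onset is handled. Stating whether the test is one- or two-sided is good practice, but it did not change the rates here. SI can stay as written.

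The cost is a sentence or two in the protocol and in the central reader's instructions; the same tracings and diary entries are used. The downside is that SAP values will be somewhat lower and, with the preceding-only option, a symptom marked just before its reflux event is no longer counted.

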2.2 Secondary objectives

- To estimate the effect over 24 hours as total values, and in upright and supine position of 4 different doses of AZD3355 compared to placebo measured as reduction in:
 - total number of reflux episodes
 - the number of acid-, weakly acidic- and weakly alkaline reflux episodes
 - the height (mean proximal extent), content (liquid, gas or a mixture) of the refluxate and esophageal pH in the pH interval 4-6.5
 - the time with esophageal pH<4
 - the time with intragastric pH<4
- To study the relationship between total number of reflux episodes, acid-, weakly acidic- and weakly alkaline reflux and GERD symptoms during 24 hours.
- To study the pharmacokinetics of AZD3355 after 30, 90, 120 and 240 mg MR 1h capsules.
- To study the relationship between exposure (area under curve (AUC)0-12h , AUC12-24h, AUC0-24h) and reflux episodes after the first and second doses of AZD3355.

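### As defined in Section 11.1.3, the symptom association probability covers acid reflux only, although the protocol names it for total, weakly acidic and weakly alkaline reflux as well

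*Protocol*

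**What the plan says.** The protocol abbreviates the symptom association probability in the same way as a statistical analysis plan, so it is called the association probability here.

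- **Objective (Section 2.2):** "To study the relationship between total number of reflux episodes, acid-, weakly acidic- and weakly alkaline reflux and GERD symptoms during 24 hours".
- **Variable (Section 11.1.1, item 10):** the objective becomes a study variable, with two indices named for it: "weakly acid or weakly alkaline reflux and GERD symptoms during 24 hours (Symptom Index (SI), Symptom associated probability (SAP").
- **Association probability (Section 11.1.3):** "consecutive two minute periods of pH recording will be analysed for the presence of reflux and symptoms". A symptom is positive if "either of the two minute periods preceding or following the start of the symptom was reflux positive (pH<4", for at least 5 seconds). Fisher's exact test gives P, the index is (1 − P) × 100%, and "a value greater than 95% is considered to support a positive correlation between symptoms and reflux".
- **Symptom Index (same section):** it is scored on the impedance/pH tracing. "Symptoms associated with a reflux event occurring within a 2 minute window before and 2 minute window after the symptom" count as positive, and no pH limit is given. A value of 50% or more supports a correlation.
- **Reflux types (Section 11.1.2):** "Weakly acidic reflux is defined as a reflux episode with an intra-esophageal pH between 4 and 6.5 lasting longer than 5 seconds". An episode counts as weakly alkaline if its pH stays at or above 6.5 throughout.

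**The concern.** The variable list attaches the association probability to all reflux types, but its definition recognises only one. This is not detail left for the statistical analysis plan. The protocol itself fixes the criterion, and anyone who follows it will produce an acid-only index.

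The population makes the gap relevant. All patients continue their PPI during the recordings (Section 5.7). Section 1.1 says their symptoms may come from acidic, weakly acidic or weakly alkaline refluxate. Section 3.2 justifies the endpoint by the belief that the drug reduces reflux of every pH class. Impedance is the signal that detects non-acid episodes, and the association probability does not use it.

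Two things are at stake. A patient whose symptoms follow non-acid reflux may be reported as showing no association. The same recording may also be positive on the Symptom Index and negative on the association probability only because the word reflux means different things in the two definitions.

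**Working it through.** The protocol states no figure to reproduce. The main check compares definitions, and a short calculation then shows what the mismatch can do.

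**Step 1. Definitions side by side**

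| Reflux type (11.1.2) | pH of the episode | Can the episode itself meet pH below 4? | Counted by the Symptom Index? |
|---|---|---|---|
| Acid | below 4 | yes | yes |
| Weakly acidic | 4 to 6.5 | no | yes |
| Weakly alkaline | never below 6.5 | no | yes |
| Total | any | acid part only | yes |

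The result holds by definition and needs no assumption. Weakly acidic and weakly alkaline episodes contribute nothing to the association probability, and total reflux is represented only by its acid part. No second association probability, by reflux type or from impedance events, is defined in the protocol.

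**Step 2. Illustration of the effect**

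Inputs from the protocol:
- Two-minute periods in 24 h: 24 × 60 / 2 = 720.
- Reflux episodes per 24 h on placebo in study D9120C00020: 30.6 / 0.61 = 50.2, about 50. The geometric mean on active treatment is in Section 12.3 and the ratio is in Section 1.3.
- Index = (1 − P) × 100%, positive above 95% (Section 11.1.3).

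Assumptions, for which the protocol gives no figures:
- 10 symptoms, 5 of them linked to reflux.
- Acid share of reflux from 0% to 60%, the same among linked symptoms.
- One period per episode, and a two-sided Fisher's exact test.

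If all reflux counts, 5 of 10 symptom periods and 45 of 710 other periods are positive, and the index is 99.97%. Under the pH rule the same recording gives:

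| Assumed acid share | Positive symptom periods | Positive other periods | Index | Above 95%? |
|---|---|---|---|---|
| 0% | 0/10 | 0/710 | 0% | no |
| 20% | 1/10 | 9/710 | 86.9% | no |
| 40% | 2/10 | 18/710 | 97.1% | yes |
| 60% | 3/10 | 27/710 | 99.4% | yes |

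If all linked symptoms follow non-acid reflux, no symptom period is positive. The index is then 0% at acid shares of 20%, 40% and 60%.

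With 5 symptoms, 3 of them linked, the index is 99.7% when all reflux counts. Under the pH rule it is 93.2%, 86.8% and 98.4% at acid shares of 20%, 40% and 60%. The uneven order comes from rounding to whole symptoms.

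**The case against.** The strongest reply is that the objective is still served. The Symptom Index accepts any reflux event. Section 6.3.1.1 has the central reader characterise individual episodes and relate symptoms to them. Item 10 names the two indices together without saying that each must be computed for every reflux type. The variable is secondary, and the synopsis mentions only symptom registration. The recordings and event markers are kept, so the index could be recomputed later.

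Most of this stands and limits the size of the point. It does not remove the mismatch. Item 10 names the association probability without restricting it to acid reflux, and Section 11.1.3 reads a value above 95% as support for a correlation with reflux in general.

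A reader might infer more than the documents support:

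- *That the objective cannot be answered.* The Symptom Index partly answers it, and the association probability still serves acid reflux.
- *That every symptom after a non-acid episode is scored negative.* A period that holds such an episode is still positive if pH also falls below 4 in it for long enough.
- *That counting reflux after symptom onset is a second error.* The window of two minutes on either side is stated consistently for both indices. The objective is a relationship and the thresholds speak of correlation, so nothing in the protocol contradicts that choice.

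**Conclusion.** The point holds as an internal inconsistency of moderate weight. As written, the association probability is an acid-only index placed under an objective that covers four categories of reflux, and it does not share a definition of reflux with the Symptom Index.

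The definitional result is exact: a weakly acidic or weakly alkaline episode can never itself satisfy the criterion. The practical size is not known from the protocol, because it depends on the acid share of reflux and on the number of symptoms. In the illustration with 10 symptoms, the conclusion changes at an assumed acid share of 20% but not at 40% or 60%.

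The primary count of reflux episodes, the Emax analysis (Section 12.2) and the sample size (Section 12.3) do not use this index and are unaffected.

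**What to change.** In Section 11.1.3, define a reflux-positive two-minute period by the presence of a reflux episode identified on the impedance/pH tracing, as the Symptom Index already does. Compute the association probability separately for any, acid, weakly acidic and weakly alkaline reflux, using the pH class the central reader assigns to each episode. Results by type will rest on few events per recording and should be read descriptively.

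The minimum alternative is one sentence stating that the association probability covers acid reflux only and that the Symptom Index alone addresses the other types, with item 10 of Section 11.1.1 worded to match.

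The cost is wording in Section 11.1.3 and in the central reader's instructions. The impedance and pH signals, event markers and diary are already collected (Section 6.3.1.1), so no new measurement is needed. Settle the definition before the blinded central reading starts, so that it is not chosen after results are seen.
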